#### **10.4.2. Safety Analyses**

All safety analyses will be performed on the safety population, defined as all participants who were randomized and received at least 1 dose of study medication.

For all safety and tolerability analyses, participants will be analyzed by the treatment received and the overall active treatment group. For active treatment, the dose received will be used.

Safety data collected at the baseline visit or the last preceding visit (if not collected at the baseline visit) will be used as the baseline value for safety analyses.

Safety measures include AEs, clinical laboratory values, physical examination findings (including body weight, height, and BMI), vital signs, and concomitant treatment usage. For quantitative variables, descriptive statistics including number of observations, mean, median, standard deviation, minimum, and maximum will be presented for observed and change from baseline values at each study visit. Qualitative variables will be summarized using counts and percentages.

Beyond the endpoints described within [Section 3](#), any additional fetal data collected will only be listed. These include but are not limited to fetal ultrasounds and antepartum fetal monitoring via NST/CTG, BPP, and fetal heart rate auscultation.

All safety and tolerability data will be presented in listings.

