AE review		X	X	X	X	X	X	AEs for mother and baby to be collected and reviewed for up to 30 days after respective dates of hospital discharge. See Section 8.3.1 for further details.

Visit Name	Screening	Treatment Period				Follow-Up		Notes
		Baseline	Weeks 1, 2, 3, etc.	Early Termination*	EOT/Delivery	F1	F2 (EOS)	
Day/Week (Window)	Day -10 to -1	0*	Every 7 Days (±1 Day) Until Delivery		Day of Delivery (+2 Days)	Phone Call: 14 Days after Delivery (±3 Days)	Clinic Visit: 28 Days after Delivery (±3 Days)	
*Participants who early terminate from study drug should still continue with weekly visits through delivery, F1, and F2.
 
Some visits may be conducted as a home health or remote visit at the discretion of the investigator upon approval by the sponsor or designee and in accordance with local and regional regulations.
 
*See Section 8.1.8 for further details on timing of baseline visit.

Fetal ultrasound	X*	X*	X**					
* First ultrasound may be done during screening OR baseline (both are not required). The first study ultrasound (screening or baseline) may be waived if an ultrasound was already performed within 1 week prior to screening and should be captured in the eCRF on the screening ultrasound page.
 
** Every 4 weeks while on study drug

Antepartum fetal monitoring (NST/CTG or BPP)		X						At baseline visit only, and thereafter at the discretion of the investigator

Visit Name	Screening	Treatment Period				Follow-Up		Notes
		Baseline	Weeks 1, 2, 3, etc.	Early Termination*	EOT/Delivery	F1	F2 (EOS)	
Day/Week (Window)	Day -10 to -1	0*	Every 7 Days (±1 Day) Until Delivery		Day of Delivery (+2 Days)	Phone Call: 14 Days after Delivery (±3 Days)	Clinic Visit: 28 Days after Delivery (±3 Days)	
*Participants who early terminate from study drug should still continue with weekly visits through delivery, F1, and F2.
 
Some visits may be conducted as a home health or remote visit at the discretion of the investigator upon approval by the sponsor or designee and in accordance with local and regional regulations.
 
*See Section 8.1.8 for further details on timing of baseline visit.

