### **Safety**

In both Part 1 and Part 2, safety assessments will include AEs, clinical laboratory tests, vital signs, and physical examinations. Additional fetal safety assessments will include serial ultrasounds to assess fetal growth and nonstress tests (NSTs)/cardiotocography (CTG) or fetal biophysical profile (BPP). Assessment of plasma concentrations of volixibat will be obtained in maternal plasma and umbilical cord plasma (when possible) at single time points, with no formal PK parameter analysis planned. PD assessments will include bile acids alongside other biomarkers.

In Part 1, ongoing monitoring of open-label safety data will be conducted by the sponsor at regular intervals per the medical and data monitoring plans as well as the routine safety surveillance activities, including but not limited to signal detection monitoring. Additionally, a chartered, independent data monitoring committee (IDMC) will review unblinded maternal and fetal safety/plasma drug level data on an ongoing basis during this study (Part 2 only), with the initial IDMC meeting (post-study start) to be held after 12 participants in Part 2 complete the study; cadence for subsequent meetings will be outlined in the IDMC charter. The sponsor plans to continue formal safety and efficacy monitoring via a chartered IDMC in Part 2; this will include AE monitoring specifications.

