### 8.4.2. Fetal Ultrasound

At screening or baseline and every 4 weeks while on study drug, a fetal ultrasound should be performed to exclude evidence of significant intrauterine fetal growth restriction or placental insufficiency. This ultrasound should include umbilical artery dopplers if indicated for estimated fetal weight <10th percentile or for other obstetric indications. Ultrasounds shall be performed and read locally.

Results should be reviewed by the investigator or qualified delegate within 1 business day. If the ultrasound demonstrates evidence suggesting new-onset intrauterine growth restriction (e.g., new finding of estimated fetal weight <10th percentile, or estimated fetal weight known to be <10th percentile before dosing with a decrease to <3rd percentile while on study drug) or evidence of new onset placental insufficiency (e.g., new onset of absent or reversed end diastolic flow), the participant should be managed according to local obstetric standard of care/best practices and the medical monitor should be notified.

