**Table 5 Analysis Visit Windows for Vitamin A, D, and E Levels and Fetal Ultrasound**

Nominal Visit	Nominal Study Day	Lower Limit	Upper Limit
Baseline	1	(none)	1
Week 4	29	2	43
Week K (K is every 4 weeks after previous visit)	$K*7 + 1$	$(K - 2)*7 + 2$	$(K+2)*7 + 1$

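### Fetal ultrasound findings are planned as listings only; a descriptive by-arm table of the findings that Protocol 8.4.2 already defines would be a cheap safety improvement

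*Protocol*

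**What the plan says.** Protocol 10.4.2 exempts the Section 3 endpoints and then states that "any additional fetal data collected will only be listed". It spells out the scope: "These include but are not limited to fetal ultrasounds and antepartum fetal monitoring via NST/CTG, BPP, and fetal heart rate auscultation".

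These are not incidental data. Under the Safety heading of Protocol 4.1, "Additional fetal safety assessments will include serial ultrasounds to assess fetal growth", together with NST/CTG or BPP, in both parts. Protocol 8.4.2 sets the schedule: "At screening or baseline and every 4 weeks while on study drug, a fetal ultrasound should be performed". The same section says what counts as a finding and what follows from it: "If the ultrasound demonstrates evidence suggesting new-onset intrauterine growth restriction" or new placental insufficiency, the participant is managed locally and the medical monitor is told. Its examples are a new estimated fetal weight below the 10th percentile, a weight already below the 10th percentile before dosing that falls below the 3rd on drug, and new absent or reversed end-diastolic flow.

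The SAP has a table titled "Analysis Visit Windows for Vitamin A, D, and E Levels and Fetal Ultrasound", but nothing in SAP Section 7 summarises ultrasound by visit or otherwise. SAP 7.6 records no deviation from the protocol's safety analyses, so the listing-only rule stands.

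For antepartum monitoring, Protocol Table 1 requires the test "At baseline visit only, and thereafter at the discretion of the investigator".

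**The concern.** Protocol 2.4 says this is the first study of volixibat in ICP, and fetal growth is one of the things the ultrasound series exists to watch. Maternal quantitative safety data are summarised by visit, and qualitative data by counts and percentages. The fetal scans are the exception. If new growth restriction were more frequent on volixibat, no planned table would count it from the scans. A reader of the study report would have to assemble the comparison from listings.

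What is at stake is how visible a fetal safety signal is in the report. The primary and secondary efficacy tests are unaffected.

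**Working it through.** The plan gives no figure on this point. Its only Part 2 sample size figure concerns sBA, and it reproduces. With 100 per arm, a difference of 10 and an SD of 25, the SE is 25 × √(2/100) = 3.54, so 10/3.54 − 1.96 = 0.87 and power is about 81% against the stated 80%. It matters here only because 100 per arm is the ceiling on the number who could be scanned.

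**1. By-arm routes already planned for fetal growth.**

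- *Adverse events.* Under Protocol 9.1.1 an abnormal scan becomes an AE only if the investigator judges it clinically significant. Such AEs are tabulated by treatment group (10.4.2.1). Protocol 8.4.2 asks for local management and notice to the medical monitor, not for an AE report. Growth restriction is neither an AESI (9.2.6) nor an ECI (9.2.7; SAP Appendix 2), so it gets no planned risk difference or exact CI.
- *Birth weight percentile.* This is an exploratory endpoint (3.4), summarised by arm (SAP 6.3) with quartiles (SAP Section 3). No endpoint counts births below a percentile.
- *Perinatal composite.* Growth restriction is not itself a component (3.2).
- *IDMC.* It sees unblinded fetal safety data in Part 2 (4.1). That serves monitoring and puts no table in the report.

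**2. What birth weight summaries could show.** For illustration, assume 10% of placebo and 20% of volixibat babies fall below the 10th percentile, with percentiles uniform within the bands 0–10 and 10–100.

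- Mean: placebo 0.10 × 5 + 0.90 × 55 = 50; volixibat 0.20 × 5 + 0.80 × 55 = 45. The shift is 5.
- Lower quartile: placebo 25; volixibat 10 + 90 × (0.25 − 0.20)/0.80 = 15.6. The shift is 9.4.

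The planned quartiles would therefore hint at a large excess more clearly than the mean. Neither is a count of affected pregnancies.

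**3. How many will be scanned.** The first scheduled post-baseline scan is at Week 4 (nominal Day 29, SAP Table 5). Protocol 4.3.2.1 expects relatively few participants on treatment beyond 3 weeks. Protocol 10.4.1.1 is less pessimistic: it expects women with sBA below 100 µmol/L not to deliver before 39 weeks. A woman randomised at 34.4 weeks, the median in the trial that 4.3.2.1 cites, would reach Week 4 at 38.4 weeks. The number scanned per arm cannot be fixed from the documents and must be shown.

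**4. Precision of the proposed table.** The approximate 95% half-width for a risk difference with equal rates p and n scanned per arm is 1.96 × √(2p(1 − p)/n). The rates and the values 30 and 50 are assumptions.

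| n per arm | p = 5% | p = 10% | p = 15% |
|---|---|---|---|
| 30 | ±11.0 points | ±15.2 | ±18.1 |
| 50 | ±8.5 | ±11.8 | ±14.0 |
| 100 (ceiling) | ±6.0 | ±8.3 | ±9.9 |

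The exact interval is generally wider. Even at the ceiling, power to detect a doubling from 5%, 10% or 15% is about 27%, 51% or 72%.

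**The case against.** The case for leaving the plan alone has four parts.

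*Other routes exist.* A reader might infer that an excess of growth restriction would never be compared by arm. The documents do not support that. Clinically significant scans can be AEs tabulated by arm, newborn AEs are all summarised (SAP 7.1.5.1 and 7.5.2), birth weight percentile is compared by arm with quartiles, and the IDMC reviews unblinded fetal data. This objection stands against the strong reading. It does not close the gap: AE capture rests on investigator judgment, and nothing counts the findings that 8.4.2 defines.

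*The table will be sparse and selected.* This stands. Women with a Week 4 scan will tend to be those randomised earlier or scanned for an indication. A reader might infer that a by-arm table on 100 per arm would expose, say, 20% against 10%. Most participants may have no scheduled on-treatment scan, and the documents give no event rates. Even with all 100 per arm scanned, 20 against 10 events gives a Fisher two-sided p of 0.073. Sparse counts are still more useful to a safety reader than a listing. The planned AESI and ECI risk differences are likewise descriptive, without formal testing.

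*Antepartum monitoring cannot usefully be tabulated.* This stands. NST/CTG or BPP is required only around the first dose and then at discretion (Protocol Table 1 and 8.4.3), and non-reassuring is given no criteria. A count of later tests would reflect who was tested.

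*The data may not be structured for it.* This is partly right. Protocol Table 1 refers to a screening ultrasound page in the eCRF, but neither document shows that estimated fetal weight percentile or Doppler result is a coded field, and scans are read locally.

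**Conclusion.** The point holds for ultrasound, as a cheap improvement to reporting. Listing-only is an explicit rule in Protocol 10.4.2 that the SAP leaves in place. It sits oddly beside a named fetal safety assessment, findings already defined in 8.4.2, and SAP windows that no summary uses. Without a change, by-arm information on fetal growth in the report is limited to AEs that investigators choose to report and to birth weight percentile summaries.

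The gap has no numerical size of its own. The added table would show only large excesses reliably: half-widths of roughly 9 to 18 points if 30 to 50 per arm are scanned and 5% to 15% have a finding, with both ranges assumed. The point does not extend to antepartum monitoring.

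**What to change.** In Protocol 10.4.2, take ultrasound out of the listing-only rule. In SAP Section 7, add one descriptive table by treatment group giving:

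- the number with at least one post-baseline scan, as the denominator, and the number already below the 10th percentile at baseline, since two findings are defined relative to it;
- the number and percentage with each 8.4.2 finding: new estimated fetal weight below the 10th percentile, fall to below the 3rd, and new absent or reversed end-diastolic flow. Note how many had a Doppler, because 8.4.2 calls for it only when indicated;
- the risk difference with the exact 95% CI (Chan and Zhang) already planned for AESIs and ECIs.

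Use the Table 5 windows to assign scans to visits, or delete the ultrasound entry if they stay unused. Label the table descriptive, with a footnote on local reading, four-weekly timing and selection. Keep all listings, and leave antepartum monitoring as listings. Separately, the monitoring schedules need reconciling: SAP Appendix 1 includes Week 1 and Protocol Table 1 does not.

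The cost is one table, with no change to sample size, alpha or visits. First confirm that the ultrasound eCRF page captures weight percentile and Doppler result as coded fields; if it does not, the local reports need coding.

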##### **10.4.2.1. Adverse Events**

In general, TEAEs are defined as AEs that start or deteriorate on or after the first dose of study medication and no later than 7 days following the last dose of study medication. For any participants (i.e., expectant mothers) who die during the study and the date of death is between the date of the first dose of study medication and the date of study discontinuation (as entered by the site), inclusive, all AEs (including those resulting in death) that occur during the study will be considered as TEAEs irrespective of the last dose and will be included in the TEAE summaries. All summaries of AEs will be based on TEAEs unless specified otherwise.

The complete list of Preferred Terms for AESIs and ECIs (as described in [Sections 9.2.6](#) and [9.2.7](#)) will be outlined in the SAP and summarized.

AEs will be coded using MedDRA. The number and proportion of participants who experience the event according to MedDRA System Organ Class (SOC) and Preferred Term will be presented by treatment group.

The incidence of all AEs and treatment-related AEs will be tabulated by treatment received. These AEs will be classified by SOC and Preferred Term using MedDRA. AEs will be graded using the CTCAE, Version 5.0, grading scale. For incidence reporting, if a participant reported >1 AE that was coded to the same SOC or Preferred Term, the participant will be counted only once for that specific SOC or Preferred Term. An overview of AEs and TEAEs, both of which include participant incidence of AEs, treatment-related AEs, AEs by severity, AESIs, ECIs, SAEs, deaths, and AEs that lead to discontinuation, will be presented.

Furthermore, exposure-adjusted incidence rates (EAIR) will be provided for each AE reported. For EAIR analyses, the following convention will be used to calculate the denominator (i.e., population-level time at-risk) for these analyses. The population-level time at-risk includes only the time each participant is at risk. The start date of at-risk time is the date of first dose of study drug, and the last date of at-risk time is the start date of the occurrence of the AE or is censored at completion/early termination, whichever is earlier.

While no formal hypothesis testing or margin selection is planned, the risk difference and corresponding exact 95% CI (using the method of Chan and Zhang [1999]) will be presented to compare treatment groups with regards to AESIs and ECIs.

Participant listings of AEs will include the dose of study medication at the onset of the event.

#### **10.4.2.2. Vital Signs and Weight/Height Measurements**

Vital signs (temperature, systolic and diastolic blood pressure, heart rate, and respiratory rate), weight, height, and BMI will be summarized descriptively by study visit and treatment group as observed and the change from baseline values.

#### **10.4.2.3. Laboratory Assessments**

Clinical safety laboratory values will be measured by a central laboratory and, where grading criteria apply, will be graded according to the CTCAE grading scale. Summary statistics for actual values and for changes from baseline will be tabulated for laboratory results by scheduled visit. Graphs of laboratory values over time may also be produced.

Participants with clinical laboratory values outside of the normal reference range at any postbaseline assessment will be summarized, including by the CTCAE and, if necessary, other grading scales. Shifts from baseline laboratory values will be tabulated. The observed vital sign data, the change from baseline, and those meeting criteria for potentially clinically significantly abnormal criteria for each measurement will be summarized with descriptive statistics.

#### **10.4.2.4. Prior and Concomitant Treatments**

Prior and concomitant treatments will be summarized descriptively by treatment group with the number and proportion of participants.

Prior medications will be presented separate from concomitant treatments. Medications that started prior to the first dose of study medication will be considered prior medications regardless

of whether they were stopped prior to the first dose of study medication. Any medications continuing or starting after the first dose of study medication will be considered to be concomitant. If a medication starts prior to the first dose of study medication and continues after the first dose of study medication, it will be considered both prior and concomitant.

Medications will be coded using the World Health Organization Drug Dictionary.

### **10.4.3. Other Analyses**

#### **10.4.3.1. Patient-Reported Outcomes**

The effect of volixibat on additional measures of pruritus efficacy and quality of life in adult participants with ICP will be evaluated via the following endpoints:

- Change from baseline in the 5-D Itch Scale
- Change from baseline in CSS
- Change from baseline in EQ-5D-5L
- Change from baseline in PROMIS SF Fatigue 7a
- Change from baseline in PROMIS SF Sleep Disturbance
- Change from baseline in PIS-Itch

Because the PROs are administered only at baseline, Week 3, and end of treatment, the change from baseline will be compared between the 2 groups with use of rank ANCOVA with adjustment for baseline with the Mann-Whitney odds as the estimand. The estimates and CIs can be calculated using the R package sanon ([Kawaguchi and Koch 2015](#)).

#### **10.4.3.2. Healthcare Utilization**

Healthcare resource utilization variables include the number and duration of medical care encounters, including surgeries and other selected procedures (inpatient and outpatient), the dates and duration of hospitalization (total days or length of stay, including duration by wards [e.g., intensive care unit]), the number and type of diagnostic and therapeutic tests and procedures, and outpatient medical encounters and treatments (including physician or emergency department visits, tests and procedures, and medications). Descriptive statistics including number of observations, mean, 95% CI on the mean, median, minimum, and maximum will be presented by visit for continuous variables. For categorical variables, the number and proportion of participants will be presented.

#### **10.4.3.3. Pharmacokinetic Analyses**

For maternal volixibat plasma concentration assessments: Plasma concentration of volixibat near predicted maximum observed concentration ( $C_{max}$ ) will be obtained during the Week 1 visit, ~3 hours after dosing. Trough plasma levels of volixibat will be obtained during the Week 3 visit before dosing. Contingent upon meaningful exposures of volixibat, PK endpoints may include but are not limited to  $C_{max}$ , time to reach  $C_{max}$  ( $T_{max}$ ), and the AUC from time zero to the last measurable time point. Actual dosing and sampling times will be used for calculation of PK parameters. Additional PK parameters may be calculated.

For fetal (umbilical cord) volixibat plasma concentration assessments: Plasma concentration of volixibat in the umbilical cord blood sample obtained at delivery will be collected (when possible) and analyzed.

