Perinatal outcomes assessment					X			
Outcomes include
 
 
• Gestational age at delivery
 
• Mode of delivery (e.g., vaginal, operative vaginal, Cesarean, etc.; and iatrogenic vs. spontaneous)
 
• Indication(s) for delivery, if iatrogenic
 
• Maternal estimated blood loss at delivery
 
• Apgar score at 5 minutes
 
• Infant/placenta weight
 
• Presence/absence of meconium staining of amniotic fluid
 
• Neonatal diagnoses and data, including NICU data if applicable
 

Umbilical cord sample (at delivery, when possible)					X			
Umbilical artery pH should be assessed first, followed by volixibat pharmacokinetics. Thereafter, sBA, total cholesterol, LDL cholesterol, and glucose can be assessed in any order.

Genetics – maternal blood (optional)		X						
Specific testing TBD. Must confirm specific consent has been obtained for genetic testing

Visit Name	Screening	Treatment Period				Follow-Up		Notes
		Baseline	Weeks 1, 2, 3, etc.	Early Termination*	EOT/Delivery	F1	F2 (EOS)	
Day/Week (Window)	Day -10 to -1	0*	Every 7 Days (±1 Day) Until Delivery		Day of Delivery (+2 Days)	Phone Call: 14 Days after Delivery (±3 Days)	Clinic Visit: 28 Days after Delivery (±3 Days)	
*Participants who early terminate from study drug should still continue with weekly visits through delivery, F1, and F2.
 
Some visits may be conducted as a home health or remote visit at the discretion of the investigator upon approval by the sponsor or designee and in accordance with local and regional regulations.
 
*See Section 8.1.8 for further details on timing of baseline visit.

Genetics – cord blood sample (optional)					X			Specific testing TBD. Must confirm specific consent has been obtained for genetic testing.
NICU admission					X	X	X	Collect NICU admissions diagnoses and data for the duration of NICU stay (i.e., follow to resolution).
Drug Levels/Biomarkers Procedures								
Volixibat concentration sample (maternal plasma)			X*	X	X			
*At Weeks 1 and 3 visit, 3 hours (±1 hour) post-dose
 
When feasible, maternal sample should be collected as close to time of actual delivery as possible.
 
Drug level sampling may be discontinued in Part 2 pending Part 1 results

Volixibat concentration sample (fetal plasma from umbilical cord at delivery, when possible)					X			Drug level sampling may be discontinued in Part 2 pending Part 1 results

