#### **Part 2: Confirmation of Safety and Efficacy with Selected Dose**

For Part 2, it is anticipated that ~200 participants (100 per arm) will be randomized after the volixibat dose is selected in Part 1. Participants with ICP with a screening sBA level  $\geq 20$   $\mu\text{mol/L}$  who also meet the ItchRO criteria (see [Section 5.1](#)) will be randomized with stratification (based on gestational age [ $<32$  weeks or  $\geq 32$  weeks] at randomization, presence/absence of gestational diabetes, and highest sBA before randomization [ $<40$   $\mu\text{mol/L}$ ,  $\geq 40$   $\mu\text{mol/L}$  to  $<100$   $\mu\text{mol/L}$ , or  $\geq 100$   $\mu\text{mol/L}$ ]) in a 2-arm (1:1), double-blind fashion to receive the selected volixibat dose BID or placebo.

Study visits to assess safety, pharmacodynamics, efficacy, and plasma concentrations of volixibat in all participants will be conducted from baseline (Day 0) until delivery at time points specified in the SoA ([Table 1](#)); sampling for volixibat concentrations may be discontinued in Part 2 if Part 1 results demonstrate consistently negligible or below the limit of quantification concentrations in maternal and umbilical cord (fetal) plasma. Because alternative measures may be implemented, when necessary, for public health or other emergency situations and when sufficient to help ensure the safety of study participants, some visits may be conducted as a home health or remote visit at the discretion of the investigator upon approval by the sponsor or

designee and in accordance with local and regional regulations. Participants will also enter ItchRO assessments into an eDiary QD. Use of limited rescue therapies for ICP will be permitted for participants who meet protocol-specified criteria.

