## 1. INTRODUCTION

This statistical analysis plan (SAP) describes the statistical analysis methods and data presentations to be used in tables, figures, and listings (TFLs) for the interim analysis as well as final analysis to support the clinical study report (CSR) for Study VLX-401. This SAP is based on the study protocol Version 1, 14 October 2020, and the electronic case report forms (eCRF). The SAP will be finalized before the interim analysis.

Any deviations from the approved protocol will be documented in either [Section 6](#) (efficacy) and/or [Section 7](#) (safety).

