## 9. PHARMACOKINETIC ANALYSES

Due to poor absorption of volixibat very low systemic exposure and plasma drug levels are expected. Volixibat plasma concentrations will be summarized using descriptive statistics by analysis visit and dose of volixibat received at the specified analysis visit.

For maternal volixibat plasma concentration assessments: Plasma concentration of volixibat near predicted maximum observed concentration ( $C_{max}$ ) will be obtained during the Week 1 visit, approximately 3 hours after dosing. Trough plasma levels of volixibat will be obtained during the Week 3 visit before dosing. Contingent upon meaningful exposures of volixibat, PK endpoints may include but are not limited to  $C_{max}$ , time to reach  $C_{max}$  ( $T_{max}$ ), and the area under the plasma concentration-time curve (AUC) from time zero to the last measurable time point. Actual dosing and sampling times will be used for calculation of PK parameters. Additional PK parameters may be calculated.

For fetal (umbilical cord) volixibat plasma concentration assessments: Plasma concentration of volixibat in the umbilical cord blood sample obtained at delivery will be collected (when possible) and analyzed.

Plasma volixibat concentrations will also be presented in participants listings.

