Perinatal outcomes assessment					X			
Outcomes include
 
 
• Gestational age at delivery
 
• Mode of delivery (e.g., vaginal, operative vaginal, Cesarean, etc.; and iatrogenic vs. spontaneous)
 
• Indication(s) for delivery, if iatrogenic
 
• Apgar score at 5 minutes
 
• Infant/placenta weight
 
• Maternal estimated blood loss at delivery
 
• Presence/absence of meconium staining of amniotic fluid
 
• Neonatal diagnoses and data, including NICU data if applicable
 

Umbilical cord sample (at delivery, when possible)					X			Umbilical artery pH should be assessed first, followed by volixibat pharmacokinetics. Thereafter, sBA, total cholesterol, LDL cholesterol, and glucose can be assessed in any order.
Genetics - maternal blood (optional)		X						Specific testing TBD. Must confirm specific consent has been obtained for genetic testing
Genetics – cord blood sample (optional)					X			Specific testing TBD. Must confirm specific consent has been obtained for genetic testing.
NICU admission					X	X	X	Collect NICU admissions diagnoses and data for the duration of NICU stay (i.e., follow to resolution).

Visit Name	Screening	Treatment Period				Follow-Up		Notes
		Baseline	Week 1, 2, 3, etc.	Early Term*	EOT/Delivery	F1	F2 (EOS)	
Day/Week (Window)	Day -10 to -1	0*	Every 7 Days (±1 Day) Until Delivery		Day of Delivery (+2 Days)	Phone Call: 14 Days after Delivery (±2 Days)	Clinic Visit: 28 Days after Delivery (±3 Days)	*Participants who early terminate from study drug should still continue with weekly visits through delivery, F1, and F2.  Some visits may be conducted as a home health or remote visit at the discretion of the investigator upon approval by the medical monitor or designee and in accordance with local and regional regulations.  *Regardless of date of screening visit, baseline visit must occur no later than 35 weeks and 0 days gestational age.
Drug Levels/Biomarkers Procedures								
Volixibat concentration sample (maternal plasma)			X*	X	X			*At Week 1 visit, 3 hours (+/- 15 minutes) post-dose; at Week 3 visit, ≤60 minutes pre-dose When feasible, maternal sample should be collected as close to time of actual delivery as possible. Drug level sampling may be discontinued in Part 2 pending Part 1 results

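### The current protocol contradicts itself on the Week 3 maternal volixibat sample: about 3 hours post-dose in the schedule, a pre-dose trough in the analysis section

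*Protocol*

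**What the plan says.** Protocol Table 1, in the row for the maternal volixibat concentration sample, sets the time as "At Weeks 1 and 3 visit, 3 hours (±1 hour) post-dose". Both visits share one post-dose window.

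Protocol Section 10.4.3.3 separates the two visits. For Week 1 it describes a "Plasma concentration of volixibat near predicted maximum observed concentration" that is "obtained during the Week 1 visit, ~3 hours after dosing". For Week 3 it says "Trough plasma levels of volixibat will be obtained during the Week 3 visit before dosing".

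SAP Section 9 carries the same Week 3 sentence, and the SAP schedule (Appendix 1, Table 7) agrees with it: "at Week 3 visit, ≤60 minutes pre-dose". SAP Section 1 gives the source: "This SAP is based on the study protocol Version 1, 14 October 2020".

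On collection, protocol Section 8.5 refers sites to the schedule of activities for the timing of plasma samples and requires the actual date and clock time of each sample. The opening of Section 8 makes adherence to the schedule a requirement of study conduct.

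On analysis, SAP Section 9 says: "Volixibat plasma concentrations will be summarized using descriptive statistics by analysis visit and dose of volixibat received at the specified analysis visit". Both documents use actual dosing and sampling times for any derived PK parameters. Protocol Section 4.1 plans single time points and no formal derivation of such parameters.

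**The concern.** One scheduled blood draw has two incompatible descriptions in the current protocol. A site that follows Table 1 samples near the expected peak. An analyst who follows Section 10.4.3.3 or SAP Section 9 takes the Week 3 value to be a trough. The planned summary, by visit and dose, would not show the difference.

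Drug level is a secondary objective in Part 1 (protocol Section 3.4, note). Section 4.4 says that dose, exposure and response will be reviewed together when the Part 2 dose is chosen, and Section 4.1 has the data monitoring committee review plasma drug levels in Part 2. A near-peak value read as a trough would overstate how much drug remains at the end of a dosing interval. If some sites instead sampled before the dose, the Week 3 row would mix two kinds of sample.

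Most values are expected to be below the assay limit, so the few quantifiable ones carry the information, and how they are read depends on when they were drawn.

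**Working it through.** The plan gives no figure to reproduce. The check sets the four statements of the Week 3 time side by side.

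| Source | Week 1 | Week 3 |
|---|---|---|
| Protocol Table 1 | 3 h ± 1 h post-dose | 3 h ± 1 h post-dose |
| Protocol 10.4.3.3 | about 3 h post-dose, near predicted maximum | before dosing, trough |
| SAP Section 9 | about 3 h post-dose, near predicted maximum | before dosing, trough |
| SAP Table 7 | 3 h ± 15 min post-dose | 0 to 60 min pre-dose |

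**Step 1: can one sample meet both?** Table 1 gives 3 − 1 = 2 h to 3 + 1 = 4 h after a dose. A pre-dose sample in the SAP window falls between τ − 1 and τ hours after the previous dose, where τ is the interval between doses. The documents give twice-daily dosing before breakfast and before dinner but no value for τ, so τ is an assumption here:

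- τ = 10 h: 9 to 10 h after the previous dose, at least 9 − 4 = 5 h later than the Table 1 window.
- τ = 12 h: 11 to 12 h, at least 11 − 4 = 7 h later.
- τ = 14 h: 13 to 14 h, at least 13 − 4 = 9 h later.

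The windows would meet only if τ − 1 ≤ 4, that is τ ≤ 5 h, which does not fit dosing before breakfast and dinner. They do not overlap.

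**Step 2: is there a second Week 3 draw?** Table 1 gives one time for the Week 3 maternal sample and no separate pre-dose sample. Both texts therefore describe the same draw.

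**Step 3: which text do sites follow?** Section 8.5 and the opening of Section 8 point them to Table 1. Samples should then be near-peak in the protocol's own terms.

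**Step 4: would the planned output reveal the timing?** The SAP summary is by visit and dose. Actual times enter only when PK parameters are derived, which is contingent on meaningful exposure. The descriptive summary does not separate samples by time since dose.

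**Step 5: can quantifiable values occur?** Section 2.5 gives a lower limit of quantitation of 0.05 ng/mL and says concentrations are typically below it. Section 2.4 gives 0.64 ng/mL as the highest concentration recorded in previous clinical studies; 0.64 / 0.05 = 12.8 times that limit. Quantifiable values are uncommon but possible.

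**Step 6: how many samples?** One Week 3 maternal draw per participant still pregnant at that visit: at most 80 in Part 1, plus Part 2 participants if sampling continues.

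**The case against.** The strongest reply is that the conflict is real but does little harm. Several parts of that reply stand.

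- No trough table, trough parameter or accumulation ratio is specified. The word trough appears only in sentences about when the sample is obtained. A reader might infer that near-peak values will be reported as troughs, or that accumulation will be misstated. The documents support neither: the SAP reports by visit and dose, and no accumulation analysis is planned. Under Table 1 the Week 1 and Week 3 samples are in fact taken at matching times.
- A reader might also infer that the conflict endangers the decision to stop sampling, since "sampling for volixibat concentrations may be discontinued in Part 2 if Part 1 results demonstrate consistently negligible or below the limit of quantification concentrations". It does not do so in the direction feared. Samples near the peak are where drug is most likely to be detected, so a mistaken finding of negligible exposure becomes less likely. A label does not move a value across the assay limit. Cord samples, which the same rule also considers, are unaffected.
- The SAP agrees with itself. Its pre-dose timing reflects protocol Version 1 and is not an independent contradiction. The core error lies between Table 1 and Section 10.4.3.3 of the current protocol; the SAP needs updating to match.
- Sample clock times are recorded, so a misread value can be identified afterwards.

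What does not stand is the suggestion that nothing needs changing. The use of actual times covers derived parameters, not the descriptive summary that is planned. Recovery after the fact also needs the time of the preceding dose. Section 10.4.3.3 presupposes that dosing times are available, but Section 8.5 explicitly requires only the sample time.

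**Conclusion.** The contradiction is established from the text alone: the current protocol gives two non-overlapping times for one Week 3 maternal sample, and no other passage reconciles them. The documents do not establish which time is intended.

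The consequence is one of interpretation. Week 3 concentrations could be read as troughs when they were drawn near the predicted peak. That bears on the Part 1 drug-level objective and on the exposure review. It has no bearing on the primary or secondary efficacy endpoints, sample size, power or Type I error.

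The conclusion assumes that sites collect by Table 1 and that whoever reads the Week 3 row relies on the analysis text for its timing. If most values are below the limit of quantitation, few will be open to misreading. The point is worth fixing because a stated rule is wrong as written and the correction is cheap, not because a major result is at risk.

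**What to change.** 1. Reconcile protocol Table 1, protocol Section 10.4.3.3, SAP Section 9 and SAP Appendix 1 Table 7 to one Week 3 maternal sampling time. The sponsor must say which was intended.
2. In SAP Section 9, classify or list each maternal concentration by actual time since the last dose, alongside visit and dose. Use the word trough only for samples confirmed as pre-dose.
3. Confirm that the time of the dose preceding each sample is captured in the case report form, since the classification depends on it.
4. For samples already drawn, apply the same classification by actual time before Part 1 concentrations are interpreted.

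The cost is wording in two documents and a small change to the PK summary. No extra samples or visits are needed. If dose times prove not to be captured, one data field would have to be added.
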